# **History of changes**

# Rev 1.

• Primary document

#### AIM

Evaluation of the safety and efficacy of the method of inhalation administration of exosomes in bilateral pneumonia caused by the new coronavirus infection SARS-CoV-2.

## **GOALS**

- 1. Develop an algorithm for introducing exosomes in case of pneumonia caused by COVID-19.
- 2. Formulate patient selection criteria for this technique.
- To analyze the safety and efficiency of exosomal administration in case of pneumonia caused by COVID-19.

## **Study Description**

Brief Summary: Coronavirus is an acute viral disease with prevailing upper respiratory tract infections caused by the RNA-containing virus of the genus Betacoronavirus of the Coronaviridae family. Most patients with severe COVID-19 develop pneumonia in the first week of the disease. As the infection progresses, the infiltration increases, and the affected areas increases. Excessive and uncontrolled immune system response with rapidly developing fatal cytokine storm plays the main role in the pathogenesis of acute respiratory distress syndrome (ARDS) due to SARS-CoV-2 infection.

> According to available data, exosomes can regulate inflammation and regenerative processes due to the change in the concentration of antiinflammatory cytokines and switch the immune cell to regenerative secretome. Inhalation of exosomes may reduce inflammation and damage to the lung tissue and stimulate the regenerative processes.

> This protocol has been developed based on the literature, information about the ongoing tests NCT04276987 (A Pilot Clinical Study on Inhalation of Mesenchymal Stem Cells Exosomes Treating Severe Novel Coronavirus Pneumonia) and NCT04384445 (Organicell Flow for Patients With COVID-19), Patent No 271036826 of 2019. "A method for obtaining and concentrating microRNA-containing exosomal multi-potent mesenchymal-stromal cells for use

in cosmetic and pharmaceutical products to stimulate regenerative processes and slow down aging.

Detailed COVID-19 is an infectious disease caused by the most recently discovered Description: coronavirus. This new virus and disease were unknown before the outbreak began in Wuhan, China, in December 2019. COVID-19 is now a pandemic affecting many countries worldwide. Globally, as of 1:09 pm CEST, 27 July 2020, there have been 16 096 741 confirmed cases of COVID-19, including 646 384 deaths, reported to WHO.

> The main and rapidly achievable target of SARS-CoV-2 is lung type II alveolar cells (AT2), which determines the development of diffuse alveolar damage. In the pathogenesis of ARDS due to COVID-19, the main role is played by an overresponse of the immune system with rapidly developing severe life-threatening cytokine release syndrome (cytokine storm). Cytokine release syndrome threatens the emergence and progression of ARDS. The key components of the pathogenesis of ARDS also include disruption of cell cytotoxicity mechanisms, excessive activation of cytotoxic lymphocytes and macrophages with a massive release of proinflammatory cytokines (FNO-α, IL-1, IL-2, IL-6, IL-8, IL-10), granulocytic colony-stimulating factor, monocytic chemoattractive protein 1), and inflammatory markers (CRP, serum ferritin), infiltration of internal organs and tissues by activated T-lymphocytes and macrophages, resulting in a hyperinflammatory reaction. Such severe lesions can lead to death or severe lung damage, including long rehabilitation after discharge.

> Experimental studies have demonstrated that mesenchymal stem cells (MSCs) may significantly reduce lung inflammation and pathological impairment resulting from different types of lung injury. Many researchers connect the antiinflammatory effect of MSC with their secretome which includes MSC derived exosomes. It is highly likely that MSC exosomes have the same therapeutic effect on inoculation pneumonia as MSCs themselves. Moreover, exosomes show a strong effect of regenerative stimulation on different wounds so the regenerative effect can be extended on patients with COVID-19 pneumonia.

The purpose of this protocol is to explore the safety and efficiency of aerosol inhalation of the exosomes in the treatment of severe patients hospitalized with novel coronavirus pneumonia (NCP).

#### **Conditions**

Conditions: Covid19

SARS-CoV-2 PNEUMONIA

COVID-19

Keywords: Covid-19

SARS-CoV-2 exosomes MSC

## Study Design

Study Type: Interventional

Primary Other

Purpose:

Study Phase: Phase 1/Phase 2 Interventional Parallel Assignment

Study Model: The trial has three groups, each with 10 subjects (n=30). All eligible study subjects

will be randomized, double-blinded, to either the two treatment groups or placebo

group.

Number of 3 Arms:

Masking: Double (Participant, Care Provider)

Two main groups will be provided with exosomes in a specially provided solution, the third group (control) will receive the same solution without exosomes. Due to exosomes are nanoparticles and requires special methods and devices to be detected the hospital staff and patients have no way to check which group receives

exosomes.

Allocation: Randomized Enrollment: 30 [Actual]

## **Arms and Interventions**

Arms	Assigned Interventions	
Experimental: EXO-1 Participants (n=10) in this group will receive standard therapy and exosomes of the first type.	Procedure/Surgery: EXO 1 inhalation Twice a day during 10 days inhalation of 3 ml special solution contained 0.5-2x10^10 of nanoparticles (exosomes) of the first type.	
Experimental: EXO-2 Participants (n=10) in this group will receive standard therapy and exosomes of the second type.	Procedure/Surgery: EXO 2 inhalation Twice a day during 10 days inhalation of 3 ml special solution contained 0.5-2x10^10 of nanoparticles (exosomes) of the second type.	
Placebo Comparator: Placebo Participants (n=10) in this group will receive standard therapy and inhalation placebo solution.	Procedure/Surgery: Placebo inhalation Twice a day during 10 days inhalation of 3 ml special solution free of nanoparticles (exosomes).	

## **Eligibility**

Minimum Age: 18 Years

Maximum 65 Years

Age:

Sex: All

Gender No

Based:

Accepts No Healthy

Volunteers:

Criteria: Inclusion Criteria:

- Ability to understand the study objectives and risks and provide signed and dated informed consent;
- Confirmed COVID-19 infection (by PCR or antibody test);
- Pneumonia requiring hospitalization, and oxygen saturation of <94% indoors or a need for auxiliary oxygen. The confirmed volume of lung damage by CT: not less than 30% and not more than 80%;
- · ability to proceed with inhalation by self;

#### **Exclusion Criteria:**

• Severe respiratory failure at the time of screening due to COVID-19 pneumonia;

- Known to undergo medical resuscitation for 14 days before randomization;
- Any serious medical condition or deviation of the clinical laboratory parameter that, in the opinion of the researcher, prevents safe participation and completion of the study by the participant Confirmed uncontrolled active bacterial, fungal, viral or other infection (other than SARS-CoV-2).
- According to the researcher, the progression to death is inevitable and will occur within the next 24 hours, regardless of the therapy.
- The life expectancy of fewer than 28 days, taking into account a medical condition already existing that cannot be corrected, e.g. participants with the following conditions or suspicions: polyorganic insufficiency, poorly controlled neoplasms, terminal stage heart disease, cardiopulmonary cardiac arrest that required cardiopulmonary resuscitation, or electrical activity not accompanied by a pulse, or asystole within the last 30 days, terminal stage liver disease, terminal stage liver disease, or liver disease;
- · Pregnancy or breastfeeding;
- Liver function failure (Class C for Child-Pugh), detected within 24 hours at screening (local laboratory);
- Absolute neutrophil count (ANC) <500 cells/µL at screening (local laboratory);

- Platelet count <50000 cells/µL at screening (based on laboratory data);

- Creatinine level ≥ 1.5 from the upper limit;
- Uncontrolled or untreated arrhythmia with clinical manifestations, myocardial infarction within the last 6 weeks or congestive heart failure (NYHA Degrees 3 or 4);
- Respiratory failure in the last 6 months or home use of oxygen in severe chronic respiratory disease (COPD);
- Quadriplegia;
- Primary immunodeficiency, tuberculosis, progressive multifocal leukoencephalopathy, aspergillosis or other invasive mold/fungal infection in anamnesis, or internal or bone marrow transplantation for 6 months before randomization;
- Known infection with hepatitis B or C viruses requiring therapy;

#### Research methods and STATISTICAL CONSIDERATIONS

Title	Purpose	Method	Frequency	Statistics
Number of	Safety	Collection of	After each	Numeric data, calculated
participants with minor and serious side effects	assessment of the procedure.	information about unwanted reactions to inhalation, for example, 1) temperature increase, 2) allergic reaction in the form of swelling Quincke, rash, seizures, etc.; 3) bronchospasm for inhalation	procedure	as a percent from whole patients in the group.
Biochemistry of blood	Evaluation of procedure efficiency	C-reactive protein, LDH	At the beginning of inhalation (day 1) and on next day of last inhalation (day 11)	The difference in each group between baseline and day 11 will be measured by T-test. The data will be presented as a Mean with full range (minmax). The difference will be calculated as Mean

				difference with Standard Deviation (SD)
Time to Clinical Recovery (TTCR)	Evaluation of procedure efficiency	Calculation of days in hospital	Once at the end of trial	The data will be presented as a Mean with Standard Deviation (SD)
SpO2 Concentration Changes	Evaluation of procedure efficiency	The concentration of SpO2 by Pulse oximetry device during procedures and compared to placebo.	Before and after each inhalation (total 4 measures per day). 10 days.	The intraday data (4 measures per day) will be calculated as a Median by day. The Median by day data (10 measures) will be processed by T-test intragroup and between groups. The data in tables will be presented as a Median (Me) with 25-75 quartile range.

The results will be statistically processed using parametric and non-parametric statistics methods using STATA version 9.0, Statistica for Windows version 6.0 and MS Office Excel 2007. Changes from the start of therapy and after will be compared using the T-test, comparing data between the main group and the control group using non-parametric method box-plot (data are presented in Me - median format with an indication of 25% (q1) and 75% (q3) quartile.

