## STATISTICAL CONSIDERATIONS

This study will enroll patients with PCR confirmed COVID according inclusion criteria.

The trial has three groups, each with 10 subjects (n=30). All eligible study subjects will be randomized, double-blinded, to either the two treatment groups or placebo group. Two main groups will be provided with exosomes in a specially provided solution, the third group (control) will receive the same solution without exosomes. Due to exosomes are nanoparticles and requires special methods and devices to be detected the hospital staff and patients have no way to check which group receives exosomes.

This is interventional, prospective, randomized double-blinded with a control group study.

The primary outcomes will be assessed at discharge of the clinic and 1 month after. Duration of study participation will be 1 months from the time of discharge from the clinic.

It is estimated that up to 2-3 research participants will be enrolled each week and that approximately 4 weeks of accrual will be necessary to enroll 10 participants.

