#### **Study Duration**

Research participants will be followed for safety for 1 months after the discharge from the clinic.

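### The only safety row collects reactions after each inhalation, and the plan does not say whether deaths, other serious events or events in the promised 1-month follow-up enter the safety percentage

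*Combined protocol and SAP*

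**What the plan says.** The table under Research methods and STATISTICAL CONSIDERATIONS has four outcome rows, and only one has a safety purpose. Its title covers "participants with minor and serious side effects". Its method is to collect "information about unwanted reactions to inhalation, for example, 1) temperature increase", followed by allergic reactions and bronchospasm as further examples. Its frequency is once following every inhalation, and its statistic is a percentage of the patients in the group. The other three rows (CRP and LDH, time to clinical recovery, SpO2) are labelled as measures of efficiency.

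Arms and Interventions schedules inhalations twice daily for 10 days in all three arms.

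Two other sections set a longer horizon. Study Duration states: "Research participants will be followed for safety for 1 months after the discharge from the clinic". STATISTICAL CONSIDERATIONS states: "The primary outcomes will be assessed at discharge of the clinic and 1 month after". Neither says what is collected after discharge or how it enters an analysis, and no outcome is designated as primary.

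The third item under GOALS is broader than reactions to a procedure: "To analyze the safety and efficiency of exosomal administration in case of pneumonia caused by COVID-19".

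**The concern.** The safety row and the safety follow-up do not meet. The row fixes what is collected (reactions to inhalation) and when (following an inhalation). A serious event that nobody regards as a reaction, a death, or any event after the twentieth inhalation has no stated route into the percentage.

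This matters because safety is a stated aim of this Phase 1/2 trial, and the Study Description itself says that the lung lesions may be fatal or cause lasting damage. If exosomes made the pneumonia worse, the resulting event could easily be put down to COVID-19 rather than to the inhalation. Comparing all events by arm is how such harm could show. A percentage restricted to inhalation reactions could look clean while events of this kind occurred, and the reader would take it as the trial's safety result.

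**Working it through.** **Inputs**
- Group size: 10 in each of 3 arms (Study Design; STATISTICAL CONSIDERATIONS). Check: 3 × 10 = 30, which reproduces the stated total. It is the only stated figure that bears on the percentage. The plan gives no event rate, alpha or power.
- Inhalations per participant: 2 per day × 10 days = 20 (Arms and Interventions).
- End of promised safety follow-up: discharge plus 1 month (Study Duration).

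**Time covered**
- Safety row: from inhalation 1 to inhalation 20, so to day 10.
- Promised follow-up: to 1 month after discharge. The length of stay is not given, so the gap cannot be stated in days. If discharge is no earlier than the last inhalation, the gap is at least 1 month.
- Other rows: SpO2 is measured "Before and after each inhalation (total 4 measures per day). 10 days", which is 4 × 10 = 40 measures. CRP and LDH are taken on days 1 and 11. Time to clinical recovery is days in hospital. None of these runs past discharge by its own definition, none defines a deterioration event, and none names death.

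**Types of event covered**
- A serious reaction to inhalation: counted, because the row's title includes serious effects and its examples are open-ended.
- A serious event not regarded as a reaction: not reached by the row's method.
- A death: named in no outcome row. Death appears only in the background and in the exclusion criteria.
- Any event after the last inhalation: not reached by the row's frequency.

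**Effect on the reported figure**
Take an arm of 10 with one death not regarded as a reaction, and no reactions. The intervals are exact (Clopper-Pearson) 95% intervals.
- Row as written, 0/10: upper limit = 1 − 0.025^(1/10) = 30.8%. Reported: 0% (0 to 30.8%).
- All events counted, 1/10: lower limit = 1 − 0.975^(1/10) = 0.25%. The upper limit solves (1 − p)^10 + 10p(1 − p)^9 = 0.025, giving p = 44.5%. Reported: 10% (0.3% to 44.5%).

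**Sensitivity to assumed rates**
Let p be the risk of a serious event in an arm and f the share of such events that falls outside the row. Both are assumptions. The chance of counting at least one event among 10 is 1 − (1 − p(1 − f))^10.

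| p | f = 0 | f = 25% | f = 50% | f = 75% |
|---|---|---|---|---|
| 10% | 0.651 | 0.541 | 0.401 | 0.224 |
| 20% | 0.893 | 0.803 | 0.651 | 0.401 |

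The table shows how the loss depends on p and f. It does not estimate either.

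**The case against.** The strongest reply is that the gap is inferred from silence. The plan promises a month of safety follow-up and assesses primary outcomes at 1 month. Of the four rows, the side-effect count is the one that fits an assessment at that time, since SpO2 and the blood tests have ended and hospital stay is fixed at discharge. On that reading, the row's frequency describes monitoring during dosing and the two later sections add to it. The row's title is also broader than its method, its examples are open-ended, and no causality step is described, so a death during dosing could be counted.

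Much of this stands. A reader might infer that the plan excludes deaths and late events by rule. The documents do not support that, because no sentence excludes them. What remains is that the only place where the safety percentage is defined limits both the type and the timing of events, and nothing links it to the later sections. Someone following the row as written would produce the narrower figure.

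Two further inferences also fail. A reader might take the worldwide counts in the Study Description (646 384 deaths / 16 096 741 cases = 4.0%) to show that a missed death is likely. That ratio is not specific to hospitalised patients aged 18 to 65 selected by these criteria, and a chance of any death among 30 is not the chance of the 0/10 versus 1/10 case. A reader might also suppose that double masking makes under-counting equal across arms. It does not: if late or unattributed events differ by arm, omitting them hides that difference.

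**Conclusion.** The point holds as a should-fix. Read literally, the safety percentage describes acute tolerability of inhalation over 10 days. It does not support a conclusion on safety through 1 month after discharge, which is the period the plan promises to observe. The table and the two later sections must be reconciled.

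No stated number is wrong and the sample size does not change. The illustrated shift, 0/10 to 1/10, is one participant in an arm. The two intervals overlap heavily, and with 10 per arm the percentage is imprecise under either definition. The frequency of such a shift is unknown because the documents give no event rate for this population. The conclusion rests on the sections available for review and on the plain wording of the row's method and frequency, not on any assumed rate.

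**What to change.** Reconcile the safety row with the Study Duration and STATISTICAL CONSIDERATIONS sections:
- Method: all adverse events, serious adverse events and deaths, regardless of attribution.
- Frequency: from the first inhalation through 1 month after discharge.
- Statistic: n/10 and percentage in each of the three arms, with inhalation reactions kept as a separate line.

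The cost is small if follow-up is still open: wording changes in the row and the follow-up text, and a few adverse-event questions at the 1-month contact already promised. The downside is that more events related to COVID-19 will be reported in all arms.

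Study Design marks the enrolment of 30 as actual, so follow-up may be complete and events that were never asked about may be unrecoverable. In that case, report every event and death recorded through 1 month, or limit the safety conclusion to inhalation reactions during the 10-day treatment period.

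### Safety is summarised only as a percentage of 10 patients per group, with no measure of precision and no estimated difference from placebo

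*Combined protocol and SAP*

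**What the plan says.** The AIM section of the combined protocol and SAP opens with "Evaluation of the safety and efficacy of the method of inhalation administration of exosomes". The third item under GOALS again pairs safety with efficiency.

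The table under Research methods and STATISTICAL CONSIDERATIONS has one safety row. Its endpoint is the number of "participants with minor and serious side effects", meaning unwanted reactions to inhalation recorded after each procedure. Its statistic is a count expressed "as a percent from whole patients in the group". The Study Design, Arms and Interventions, and STATISTICAL CONSIDERATIONS sections all put 10 patients in each of two exosome groups and one placebo group, 30 in total.

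The general text below the table uses T-tests for change from the start of therapy. For contrasts between groups it describes "comparing data between the main group and the control group using non-parametric method box-plot", with medians and quartiles. The Study Duration section adds: "Research participants will be followed for safety for 1 months after the discharge from the clinic". No statistic is attached to that follow-up.

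The documents give no confidence level, acceptable event rate, safety decision rule, pooling of the exosome groups or derivation of the sample size.

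**The concern.** With 10 patients per group, each affected patient moves the result by 10 percentage points. A table following the plan would show figures such as 0%, 10% and 0% with nothing to indicate their uncertainty. The general methods do not fill the gap, because a T-test on change and a box-plot of medians and quartiles are not suited to a yes/no outcome per patient. The SpO2 row of the same table does name a between-group analysis; the safety row does not.

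At stake is how far the trial's safety statement can go. The randomised, blinded placebo arm inhales the same solution without exosomes, so it is the natural reference for what the exosomes add. The plan produces a placebo percentage but no estimate of the difference from it and no indication of how well that difference is known.

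**Working it through.** **Inputs.** n = 10 per group and three groups (STATISTICAL CONSIDERATIONS). The safety statistic is a percentage of the group (Research methods table). The 95% level is an assumption; two-sided limits are the main case and one-sided limits show the range.

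**The plan's own figure.** 3 × 10 = 30 agrees with the stated total. The plan gives no event rate, interval width or power, so nothing more can be reproduced.

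**Step 1: precision per group.** The exact (Clopper-Pearson) limits for x events in n are: lower = 2.5% quantile of Beta(x, n − x + 1), taken as 0 when x = 0; upper = 97.5% quantile of Beta(x + 1, n − x).

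For x = 0 the upper limit reduces to 1 − 0.025^(1/n). With n = 10 this is 1 − 0.025^(0.1) = 0.308.

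| Events | Reported by the plan | Exact two-sided 95% interval | One-sided 95% upper limit |
|---|---|---|---|
| 0/10 | 0% | 0% to 30.8% | 25.9% |
| 1/10 | 10% | 0.3% to 44.5% | 39.4% |
| 2/10 | 20% | 2.5% to 55.6% | 50.7% |
| 3/10 | 30% | 6.7% to 65.2% | 60.7% |

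Other upper limits for 0/10 are Wilson 27.8% and rule of three 3/10 = 30%. Across these methods the limit for zero events runs from 25.9% to 30.8%.

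**Step 2: chance of seeing no event.** P(0/10) = (1 − p)^10. This is 0.90^10 = 34.9% at a true rate of 10%, 0.80^10 = 10.7% at 20%, and 0.70^10 = 2.8% at 30%. These probabilities follow from the group size, and reporting an interval does not change them.

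**Step 3: difference from placebo.** At 0/10 versus 0/10, a Wald interval has zero width because both estimated variances are zero. The Newcombe interval combines the Wilson limits. For zero events the Wilson limits are 0 and z²/(n + z²) = 3.84/13.84 = 0.2775. The interval is therefore 0 ± √(0² + 0.2775²), or about −28 to +28 percentage points.

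**Step 4: would a test serve instead?** With 0/10 on placebo and x/10 on one exosome type, the two-sided Fisher p-value is 2 × C(10, x)/C(20, x). For x = 4 it is 2 × 210/4845 = 0.087. For x = 5 it is 2 × 252/15504 = 0.033. Five of 10 patients would need an event before p fell below 0.05, so estimation with an interval is more informative than a test.

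**Step 5: pooling the exosome groups (not planned).** For 0/20 the upper limit is 1 − 0.025^(1/20) = 16.8% two-sided, or 13.9% one-sided. This assumes that both exosome types have the same rate. If only one type carries a 10% risk and the other carries none, the chance of seeing no event in either arm stays at 34.9%; it falls to 0.90^20 = 12.2% only if both types carry that risk.

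**The case against.** Descriptive safety counts by arm are a legitimate analysis in a 30-patient Phase 1/2 study. The group size is stated openly, so a reader can work out each per-arm interval. No estimate is biased, and ten per group is not itself an error. All of that stands, and it makes this a gap in reporting rather than a wrong analysis.

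Three stronger readings are tempting, and the documents do not support them:

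- *Safety will be reported without a comparator.* The percentage is calculated in each group, so the blinded placebo figure will stand beside the two exosome figures. What is missing is an estimated difference with its precision. The documents also do not say how often the listed reactions would arise from the disease alone.
- *No events will be declared safe.* No section sets such a rule or an acceptable rate. The documents leave the interpretation open.
- *Zero or few events leave rates of about 30% open.* That figure fits zero events only. One or two events leave 44.5% or 55.6%.

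The objection does not answer the remaining gap. Nothing in the plan obliges the report to show or interpret an interval, and the general methods offer none suited to a binary outcome.

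**Conclusion.** The point holds as a proportionate, nearly free improvement. Safety shares the aim with efficacy, yet it is summarised only by a percentage of 10 patients, without precision and without an estimated difference from placebo. At an assumed two-sided 95% level, zero events in a group exclude only rates above 30.8% (25.9% one-sided). One event excludes only rates above 44.5%, and two only those above 55.6%. With no events in either of two arms, the difference from placebo is known only to within about 28 points each way.

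The conclusion does not depend on the choice among the standard methods shown. It does not imply that the planned percentages are wrong or that more patients are needed.

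**What to change.** Amend the safety row, or the analysis text that supports it, as follows:

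1. Count participants with at least one event, separately for any and for serious events, and report the count and percentage per arm with an exact Clopper-Pearson 95% interval.
2. For each exosome arm, report the risk difference from placebo with a score-based 95% interval, naming the method (for example Newcombe). Do not use Wald, which has zero width at 0/10 versus 0/10.
3. Word the safety conclusion as the rate excluded per arm. For example, if no events are seen in an arm, rates above 30.8% in that arm are excluded at the two-sided 95% level.
4. Show a pooled exosome figure only as a secondary summary, labelled as assuming a common rate for the two exosome types, always beside the per-arm limits and never in place of them.
5. State the confidence level and sidedness.

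The cost is a few lines of text and some table programming, with no additional data or patients. The Study Design section gives enrolment as an actual figure, so if results are already known the intervals should be labelled as added after the plan.

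### Neutrophils, platelets, creatinine and liver function limit entry but are not scheduled again, so symptom-free laboratory toxicity would not be systematically captured or compared between arms

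*Combined protocol and SAP*

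**What the plan says.** The Exclusion Criteria of the combined protocol and SAP set four laboratory-based entry limits:

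- neutrophils: "Absolute neutrophil count (ANC) <500" cells/µL at screening;
- platelets: "Platelet count <50000" cells/µL at screening;
- creatinine: "Creatinine level ≥ 1.5 from the upper limit", with no time point given;
- liver: "Liver function failure (Class C for Child-Pugh), detected within 24 hours at screening (local laboratory").

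A further criterion excludes patients with a laboratory deviation that the investigator thinks makes participation unsafe.

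After entry, the table under Research methods and STATISTICAL CONSIDERATIONS is the only measurement schedule. Its one laboratory row lists "C-reactive protein, LDH", timed "At the beginning of inhalation (day 1) and on next day of last inhalation (day 11"), with the purpose "Evaluation of procedure efficiency". Its one safety row counts participants with side effects, minor or serious. These are gathered after each procedure as unwanted reactions to the inhalation, with fever, allergic reaction, seizures and bronchospasm as examples. Study Duration adds safety follow-up for one month after discharge and names no visit, test or method.

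**The concern.** Safety comes first in the stated aim, and the trial is labelled Phase 1/Phase 2 with two exosome products. The protocol itself ties laboratory values to safe participation at entry, then does not return to them after exposure. A symptom-free fall in platelets or rise in creatinine is not something that staff or patient would notice after an inhalation, and no planned table would hold it.

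COVID-19 can itself disturb these values, so single abnormal results are hard to interpret without a concurrent control. The trial has a randomised placebo arm that could supply that context, but the plan does not use it for this purpose. A favourable safety statement would then rest on observed reactions alone, and a reader might not notice the limit.

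**Working it through.** The plan gives no figure to reproduce on this point. The check sets the entry limits against the schedule and then asks what measurement could show at this sample size.

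**Inputs from the documents**

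- Arms and Interventions: two inhalations a day for 10 days, so 2 × 10 = 20 inhalations.
- Study Design: three arms of 10, so 3 × 10 = 30 patients, of whom 2 × 10 = 20 receive an exosome product.

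**Entry limits against the later schedule**

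| Domain | Limit at entry | Planned measurement after entry |
|---|---|---|
| Neutrophils | Yes | None |
| Platelets | Yes | None |
| Creatinine | Yes | None |
| Liver function | Yes (Child-Pugh class C) | None |
| CRP, LDH | No | Days 1 and 11, as efficacy |

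None of the four domains has a planned value after baseline, and no planned laboratory result has a safety purpose. Adding the four domains to the day-11 sample would give 4 × 30 = 120 domain-level results.

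**What those results could show**

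The rates below are assumptions, because the documents give none. They also assume no background abnormality, which is optimistic in COVID-19.

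Chance of at least one case: 1 − (1 − p)^n.

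| Assumed true rate p | One arm, n = 10 | Both exosome arms pooled, n = 20 |
|---|---|---|
| 5% | 1 − 0.95^10 = 40% | 1 − 0.95^20 = 64% |
| 10% | 1 − 0.90^10 = 65% | 1 − 0.90^20 = 88% |
| 20% | 1 − 0.80^10 = 89% | 1 − 0.80^20 = 99% |

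The per-arm column is the relevant one, since EXO-1 and EXO-2 are different products. Pooling is a secondary view.

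One-sided 95% upper bound when no case is seen: 1 − 0.05^(1/n).

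- n = 10: 1 − 0.05^(1/10) = 25.9%.
- n = 20: 1 − 0.05^(1/20) = 13.9%.

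Formal comparison is weak. Take 4 of 20 exosome patients against 0 of 10 on placebo. With 4 cases among 30, the probability that k fall in the placebo arm is C(10,k) × C(20,4−k) / C(30,4). For k = 0 this is 4845/27405 = 0.177. The other tables no more likely than that are k = 3 (2400/27405 = 0.088) and k = 4 (210/27405 = 0.008). The two-sided Fisher p is 0.177 + 0.088 + 0.008, about 0.27.

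**The case against.** A reader might infer that organ or blood toxicity cannot appear in the safety result at all, or that there are no post-exposure data on any organ system screened at entry. The documents do not support either reading. The safety row covers serious as well as minor effects, its examples are open-ended and include a systemic event (seizures), and safety follow-up runs for a month after discharge. Toxicity with clinical signs could therefore be reported and counted. Respiratory status is also screened at entry, and SpO2 is measured before and after every inhalation. LDH on day 11 may rise with tissue damage, although it is non-specific and assigned to efficacy.

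It can also be said that limits meant to keep out gravely ill patients do not commit a plan to the same variables as toxicity endpoints, and that nothing in the documents names marrow, kidney or liver as an expected target of an inhaled product. That is fair: the choice of assays is a design judgement. But the investigational products are being studied partly for safety, and the plan itself regards these values as relevant to taking part.

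Hospital care may well produce such tests anyway. The plan neither collects nor tabulates them, and ad hoc testing can differ by patient and arm.

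Finally, ten patients per arm cannot establish or exclude a difference. That stands, and it is why the added data should be reported descriptively.

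**Conclusion.** The point holds in a limited form. The plan measures no neutrophil count, platelet count, creatinine or liver test after entry, so symptom-free changes in these would not be systematically captured or compared between arms. It does not follow that the trial is blind to all organ toxicity, since events with clinical signs can still be counted.

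What is lost is modest but real. At assumed rates of 10% or 20% and with no background abnormality, measurement would give a 65% or 89% chance of at least one case per product arm (88% or 99% if the two products are pooled). It would not demonstrate safety: zero cases leaves a one-sided 95% upper bound of about 26% per arm, or 14% pooled. The gap is worth closing because the remedy is cheap and changes what the safety result can say.

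**What to change.** - Measure neutrophils, platelets, creatinine and routine liver tests at the existing day-1 and day-11 blood collections, or at last contact if that comes earlier. A day-1 value is safer than relying on screening results, because the plan does not say that those are kept as trial data and the creatinine criterion names no time point.
- Add to the safety row a table by arm of change from baseline for each test.
- Give the number of patients newly crossing the entry limits as a secondary count only. Those limits are extreme and would miss moderate shifts, and Child-Pugh is a class, not a single test.
- State that the table is descriptive, and report the upper bound alongside any zero count.
- Study Design lists enrolment as actual. If data collection is complete, retrieve any available hospital values, say how complete they are in each arm, and limit the safety conclusion to clinically observed reactions.

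Cost: if collection is still open, a protocol amendment and a few routine assays for 30 patients on blood already being drawn. The downside is some COVID-related abnormalities to tabulate in every arm. Clinical handling of an abnormal value is for the sponsor and investigator.
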